Best practice for establishing effectiveness through an RCT requires a step-wise approach: (1) a feasibility study to address specific elements of the RCT (e.g., intervention characteristics); (2) a pilot RCT to address barriers and inform parameters of the main RCT; and (3) a main RCT to assess effectiveness (15). The current protocol describes a non-randomised, single-arm feasibility study (step 1 above), with the aim to assess feasibility, identify and rectify problems, and increase the success of a future evaluative RCT.

Objectives

The primary objective of the current study is to assess the feasibility and other methodological components of the Love Together, Parent Together (L2P2) intervention to inform the parameters of a future pilot (step 2 above) and main RCT (step 3 above). L2P2 is a brief conflict reappraisal program for couples with young children designed to support whole family functioning. Primary objectives of the current feasibility study are as follows:

(1) *Recruitment*: Establish partnership with three recruitment sources and provide examine recruitment rates to determine if additional recruitment sources are needed.

(2) *Sample*: Assess whether our recruitment approach and eligibility criteria are appropriate for the intended sample (i.e., participants with mild to moderate levels of couple distress as in a secondary preventive intervention). Relatedly, we are interested in the heterogeneity of the sample obtained through this recruitment approach based on sample demographics including income/education level, racial/ethnic identification, immigration status and history, and sexual orientation/gender identity.

(3) *Program*: Assess program retention, adherence, and uptake rates—that is, the extent to which participants complete the assessment schedule in full, engage in the three writing (intervention) sessions, and report use of conflict-reappraisal strategies in between sessions.

(4) *Measurement*: Conduct a preliminary validation of a primary outcome measure of couple “we-ness” (16) based on a content analysis of writing samples collected during the intervention. This new measure will be used in conjunction with pre-existing self-report measures of perceived partner responsiveness and responsiveness towards one’s partner for a multi-method/multi-informant assessment approach in subsequent pilot/main RCTs.

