Eligibility criteria are as follows: (i) both participants endorse being in a relationship; (ii) partners reside in the same home; (iii) one or more children under the age of 6 living at home; (iv) both participants are over age 18 years; and (v) both members of a couple agree to participate. Exclusion criteria included: (i) no current plans or history of separation or divorce as this is meant to be a secondary preventative intervention for couples experiencing mild-to-moderate but not severe relationship difficulties.

Recruitment sources include: (1) Moms at Work, a community, education and advocacy group supporting women in their careers; (2) Unemployed Help Centre of Windsor Inc., a nonprofit organization assisting the un/underemployed and disadvantaged person during the transition period in the reemployment process; and (3) EarlyOn Child and Family Centres, who offer free, high-quality programs for young families. These recruitment sources were selected to get a range of participants in terms of potential risk factors for relationship problems.

Listsers members from each recruitment source will receive an invitation to participate in research with a direct contact link to the L2P2 study platform via Qualtrics. Participants will go through an eligibility screen, followed by review of a letter of information and informed consent. Once participants have consented, they will be asked for their contact information and that of their partner (if they are the first member of the couple to sign up). The second member of the couple will be contacted directly by the study team via email with an invitation to enroll. Once both members of a couple have enrolled, they will be given couple and participant IDs, and a survey schedule will be set-up and executed. For a schematic diagram of the time schedule of enrolment, intervention, and assessments, see Figure 1.

Intervention

Given that this is a single-arm design, only an intervention group will be described. The intervention sessions will consist of two stages. First, participants will be asked to provide a "summary of a time when you and your romantic partner did not agree in the last two weeks..." focusing on "you and your partner's actions (what you said and did), not about what you were thinking or feeling." Second, participants will be asked to engage in a writing task wherein they

will be instructed to reappraise the conflict they previously reported based on the following prompts (14):

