Several steps will be taken to improve adherence to intervention protocols. The current feasibility study will be conducted online to reduce barriers to participation. The survey and intervention sessions will be made available for mobile and/or computer users to enhance access and promote adherence. Remuneration of participants will occur as the study progresses (i.e., after each session) via email in the form of a choice of gift card. Specifically, each participant will receive \$5.00 for the baseline survey, \$10.00 for each of the three intervention sessions, and \$5.00 for the post-intervention survey (\$40.00 per participant for full participation). Reminders of study timelines and survey/intervention session expiry dates will be provided by email.

Outcomes and Analysis

Table 1 presents all study objectives with associated outcomes, and criteria for success of feasibility, hypothesis for secondary outcomes, and methods of analyses, when applicable. Feasibility outcomes will be reported descriptively using descriptive statistics, means (standard deviations) and frequencies/percentages. Analyses for pre-post change and validation of an objective primary outcome measure are described in Table 1. If success indicators are not met, we will make changes to study design accordingly (e.g., expand recruitment sources, adjust eligibility criteria, adapt intervention schedule and/or compensation). Analyses will include all

participants who complete baseline assessments, using Bayes estimation, which is more robust with small sample sizes.

Sample size:

We chose the sample size of 20 couples (with expected attrition), with the goal of having data for 15 couples (N = 30). This will allow us to examine rates of recruitment over several weeks, appropriateness of eligibility criteria and reasons for exclusion, diversity of sample, retention, adherence, and uptake, as well as preliminary analyses examining pre-post change and the validity of a new primary outcome measure.

The current protocol does not include stopping or discontinuing guidelines.

Data Management

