No data entry is required as participants provide responses directly into Qualtrics. Study protocols have been developed by the Principal Investigator (PI: first author) which outline clear steps for enrolling study participants and scheduling surveys and compensation schedules. Data quality checks will be conducted at regular check points throughout data collection by the PI. Steps will be taken to ensure linking of participants within couples and over time and independent completion of surveys. Embedded data will be used across surveys to ensure consistency in reporting on specific children. Range checks will be conducted on all data to ensure valid values.

Ethics and dissemination

Ethics approval has been granted by York University (Certificate #: e2021-266). Changes to the protocol will be reported in the publication of study findings. Informed consent will be completed online (see additional file 2).

All information provided by participants will be kept private and confidential. An electronic file linking participant contact information with their couple identification numbers will be only accessible by the PI (first author) and research coordinator. Qualtrics servers will contain email addresses linked to each participant's data to allow for communication with participants (i.e., sending out reminders and surveys). Any data shared with the research team will contain only the participant codes, and will be securely transferred using an encrypted email or secure server.

All study data will be temporarily stored on Qualtrics before anonymized records are sent to York University secure servers (OneDrive). Qualtrics is protected by high-end firewall systems. Qualtrics uses Transport Layer Security (TLS) encryption (also known as HTTPS) for all transmitted data. Anonymized data will be made available to the senior investigators (first, second, and senior authors), and their research assistants and students (current and future) under the direct supervision of the research team.

We will destroy any personally-identifiable data at the end of the study. We will keep non-identifiable data to comply with open science and data sharing practices, as well as to allow for future analysis of data.

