The current feasibility study is funded by York University, Faculty of Health, with generic funds provided to the Principal Investigator ([name]). Funders have no role in the project, including in study design, collection, management, analysis, and interpretation of data, writing of the report, and/or decision to submit the report for publication.

Authors' contributions

HP: Study conceptualization and design, oversight of the development of the study protocol, survey development, recruitment, and data collection, initial draft of the manuscript.

AM: Study conceptualization and design, substantive revision of the manuscript.

VB: Development of the study protocol, survey development, and substantive contributions to the drafting of the manuscript.

LT: Study conceptualization and design, substantive revision of the manuscript.

MW: Study conceptualization and design, substantive revision of the manuscript.

All authors have approved the submitted version of the manuscript and have agreed to be personally accountable for their contributions.

Acknowledgements

Thank you to Drs. [name], [name], and [name], for their consultation on study design. In addition, thank you to [name] for critically reviewing the study protocol and survey development, and to [name] for her coordination of the project.

Authors' information (optional)

Not applicable.

Tables

Table 1

Primary Objectives To Determine:	Outcome	Criteria for 'success' of feasibility/hypothesis	Method of analysis
Recruitment	Number of participants Accessed (I.e., initiate registration) per week, stratified by recruitment source	10 couples per week over the course of 4 weeks who access our registration site	Descriptive statistics
	Number of participants Enrolled per week, stratified by recruitment source	5 couples per week over the course of 4 weeks who enroll in the study	
Eligibility criteria	% interested participants that meet Inclusion Criteria (with reasons for exclusion)	< 50% of participants are excluded for any one criterion.	
Sample diversity	% participants income <= regional median, <= high school degree	> 30% of our sample has 1+ indicator.	
Sample diversity (race/ethnicity/immigration)	% participants racialized, immigrant	> 30% of our sample has 1+ indicator.	
Sample diversity (sexual orientation/gender)	% participants non-heterosexual, gender non-conforming	> 30% of our sample has 1+ indicator.	

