Mild-moderate risk for relationship distress	% participants scoring 'clinical' (>13) on the Dyadic Adjustment Scale (20) % participants scoring 'high' (>29) on the COVID-19 Family Stressor Scale (21)	< 50% of eligible participants.	
Participant retention	% participants who remain in study until end of post-intervention assessment	> 90% of participants	
Participant adherence	% participants who complete 2/3 intervention sessions	> 90% of participants	
Participant uptake	% participants reporting some use of conflict reappraisal outside of sessions	> 80% of participants	
Acceptability	% of participants reporting at least 'good' on 80 % or more indicators on an Implementation Acceptability Scale assessing attitude, burden, perceived effectiveness, and ethicality (22).	> 80% of participants, (stratified by gender, immigrant status, and racialized groups)	

Primary outcome measure development	Objective assessment of wellness (16) based on content analysis of writing samples. Will include an analysis of first-person plural pronouns (we, us, our, ours), reference to partners' internal states (beliefs, desires, intentions), and positive affective language (23)	Inter-rater reliability (Cronbach's alpha > .80) Internal consistency (Cronbach's alpha > .70) Significant group differences between male and female participants based on t-tests ($p < .05$) Significant correlations ($p < .05$) with indices of convergent validity (i.e., self-reported responsiveness, partner reported perceived partner responsiveness).	

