Secondary objective To Explore: Pre-Post Change in Outcome Measures	
Couples' Relationship Quality: Perceived Relationship Quality Scale (24)
 
Conflict-Related Negativity: two items following fact-based summary: "I was angry at my partner for his/her behavior during this conflict," "My partner's behavior during this conflict was highly upsetting to me" (14).
 
Perceived Partner Responsiveness/Responsiveness Directed Towards Partner: Two eight-item scales will assess participants' perceptions of their partners responsiveness/insensitivity and their own responsiveness/insensitivity towards their partner, respectively (25)
 
Parent-Child Relations, Parenting Practices Scale from the Ontario Child Health Study (26)
 
Parent Mental Health, K10 Psychological Distress Scale (27)
 
Child Emotional and Behavioural Problems, Pediatric Symptom Checklist (Baby, Preschool, and Standard versions) (28)
	Intervention will improve outcomes from baseline to post-intervention surveys	3-level multilevel models, similar to regression analysis but accounting for clustering within data structure

Figures

Figure 1

Schedule of enrolment, intervention, and assessments.

	Study Period					
	Enrolment	Post-Enrolment				
TIMEPOINT	$-t_1$	t_1 Week 0	t_2 Week 1	t_3 Week 3	t_4 Week 5	t_5 Week 6
ENROLMENT:						
Eligibility screen	X					
Informed consent	X					
Contact Information	X					
Allocation						
INTERVENTIONS:						
[Intervention A]			X	X	X	
ASSESSMENTS:						
Demographics, COVID-19 Stress, Relationship Distress		X				
Couples' relationship quality, perceived partner responsiveness, responsiveness to partner, parent mental health, child mental health, parent-child relations		X				X
Conflict-Related Negativity			X	X	X	
Use of Conflict Reappraisal Strategy				X	X	
Acceptability						X

References

2. Kluwer ES. From partnership to parenthood: A review of marital change across the transition to parenthood. *Journal of Family Theory & Review*. 2010;2(2):105-25.

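### The male-female t-test in the we-ness row of Table 1 makes no use of the couple pairing and, if partners' scores are positively correlated, gives away power

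*Protocol*

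**What the plan says.** The Outcomes and Analysis section of the Protocol points to one place for this analysis: "Analyses for pre-post change and validation of an objective primary outcome measure are described in Table 1". In Table 1, the row on primary outcome measure development sets four criteria: inter-rater reliability, internal consistency, "Significant group differences between male and female participants based on t-tests" at p < .05, and correlations at p < .05 with the participant's own reported responsiveness and with the responsiveness that the partner perceives. The we-ness score is "based on a content analysis of writing samples collected during the intervention" (Objectives, item 4).

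Three other places bear on the structure of the data:

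- Eligibility criterion (v) under Participants requires that "both members of a couple agree to participate". The Sample size section aims for data from 15 of 20 couples and counts them as 30 people.
- Data Management states: "Steps will be taken to ensure linking of participants within couples and over time and independent completion of surveys".
- The next row of Table 1, on pre-post change, specifies multilevel models "accounting for clustering within data structure".

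The method cell of the we-ness row is blank in the text available to me. That may come from the PDF conversion, so nothing here rests on it.

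**The concern.** We-ness is a property of a couple, and both partners write about disagreements with each other. It is therefore plausible, though the Protocol does not say so, that their scores are correlated. A two-sample t-test takes the variance of the male-female difference to be the sum of two independent parts. If the correlation is positive, that variance is overstated: the test rejects too seldom and misses real differences that the same data could show.

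The Protocol allows for clustering in the exploratory pre-post row but not in this row, which serves one of its primary objectives. The measure is meant for the later pilot and main trials, and the Protocol says that unmet success indicators lead to design changes. What is at stake is how far this criterion can be trusted.

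**Working it through.** **Inputs from the Protocol.** 15 couples expected and 20 enrolled, two people per couple, threshold p < .05. There is no power calculation to reproduce. The counts are consistent: 15 × 2 = 30 people, and 15/20 implies 25% attrition.

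**Assumptions.** Two-sided tests, normal scores with equal variance in men and women, one we-ness score per person, true difference d = 0.5 SD, and within-couple correlation ρ from -.3 to .7. The Protocol gives neither d nor ρ.

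**Why the two tests differ.** With n opposite-sex couples, the variance of the difference in means is 2σ²(1 − ρ)/n. The two-sample test takes it as 2σ²/n. Its standard error is thus too large by a factor 1/√(1 − ρ), which at ρ = .5 is 1/0.707 = 1.41.

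**Paired power, one case in full.** The standardised paired effect is d/√(2(1 − ρ)). At ρ = .5 this is 0.5/√1 = 0.5. The noncentrality is 0.5 × √15 = 1.94, the critical value on 14 df is 2.145, and the noncentral t gives power 0.44.

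**Results, 15 opposite-sex couples** (two-sample figures by simulation, paired power from the noncentral t):

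| ρ | Size, two-sample | Power, two-sample | Power, paired |
|---|---|---|---|
| -.3 | 8.4% | 29% | 20% |
| .1 | 3.9% | 25% | 27% |
| .3 | 2.2% | 23% | 33% |
| .5 | 0.8% | 20% | 44% |
| .7 | 0.1% | 15% | 64% |

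The paired test holds its size at 5% throughout. With 20 couples and ρ = .5, power is about 29% against 56%.

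**Same-sex couples.** These place both partners in one group, which works against the conservatism. Table 1 also seeks "participants non-heterosexual, gender non-conforming" as a diversity target, so they are to be expected. With 4 same-sex couples among 15 and ρ = .3/.5/.7, the two-sample size is 3.6/2.7/1.7% and its power is 25/25/24%, against 31/38/54% for a couple-level model. With 8 of 15, the size is near nominal (5.3/5.5/5.8%), but power is still lost at .5 and .7 (28% and 28%, against 32% and 43%).

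**Pooled correlations.** When all 30 people are pooled and the true correlation is zero, the variance of r is inflated by about 1 + ρxρy, where ρx and ρy are the within-couple correlations of the two measures. At .5/.5 this is 1.25, and 1.96/√1.25 = 1.753, which gives a two-sided size of 8.0%. Simulation with 15 couples gives:

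| ρx/ρy | Type I error |
|---|---|
| 0/.5 | 5.0% |
| .1/.1 | 5.1% |
| .3/.3 | 6.0% |
| .3/.5 | 6.7% |
| .5/.5 | 8.0% |
| .7/.7 | 11.2% |

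**The case against.** The strongest objection is textual. The Protocol never says that the samples are treated as independent. A paired t-test is also a t-test, the plan is to link partners, and the choice between the two forms is often left to an analysis plan. This stands in part: the two-sample test is an inference from the reference to group differences. But the Protocol itself sends the validation analysis to Table 1, and the row there fixes the test and the threshold with no mention of couples. Even if pairing was intended, the row does not say so, and the choice changes the result.

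A second objection is size. The contrast of 44% with 20% needs ρ = .5, d = 0.5 and opposite-sex couples only. At ρ = .1 it is 27% against 25%. This stands, and it limits the severity.

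A third is that the correlations hardly need repair. A couple-level association model has a size of 5.6 to 5.9% with 15 couples, so it brings no size gain up to about .3/.3 and is slightly worse when the within-couple correlations are low. Its result also depends on which variable is the outcome: at a true r of .4, the two choices disagree on p < .05 in 8% of studies at .1/.1, .3/.3 and .5/.5, and in 14% at .1/.5. This stands, so the correlations are only a secondary part of the point.

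A reader might go further and infer that the measure would be wrongly dropped, or that both criteria are invalid. The Protocol supports neither. It calls the validation preliminary, states no rule that combines the criteria, and does not say that failing one removes the measure.

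**Conclusion.** The point holds for the male-female comparison, on the natural reading of the row and if partners' we-ness scores are positively correlated. At assumed correlations of .3 to .7 with 15 opposite-sex couples, the two-sample test has a true size of about 2% down to 0.1% and loses roughly 10 to 49 percentage points of power at d = 0.5 (33 − 23 = 10; 64 − 15 = 49). The loss is negligible at .1 and smaller when some couples are same-sex. At -.3 the direction reverses and the test is liberal, at about 8%.

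The correlation criterion is a minor addition: about 6% at .3/.3 and 8% at .5/.5, with no inflation if either measure is uncorrelated within couples.

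The consequence is a less reliable success criterion in a feasibility study, not a wrong trial decision. Severity is minor to moderate.

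**What to change.** Amend the we-ness row of Table 1 and leave its thresholds as they are.

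1. **Gender difference.** State that it is tested at the couple level at p < .05: by a paired t-test if all couples are opposite-sex, otherwise by a linear model with an exchangeable (compound-symmetric) covariance for the two partners and degrees of freedom equal to the number of couples minus 1. With opposite-sex couples only, the model reproduces the paired test. It also admits same-sex couples, which a paired test cannot use. Its simulated size with 15 couples is 4.9 to 5.1% with none same-sex and 5.1 to 5.8% with 4. A random couple effect with variance held at or above zero is not a full substitute: at ρ = -.3 its size is 7.4%, against 4.9% with the exchangeable covariance.
2. **Convergent validity.** Keep the correlation as the estimate and the criterion. If its p-value is to allow for couples, name one couple-level model in advance, with we-ness as the outcome and responsiveness as the predictor. Expect no gain in size unless both within-couple correlations are about .3/.5 or more.
3. **Bayesian estimation.** The Outcomes and Analysis section says in general terms that analyses use Bayesian estimation. State that these p < .05 tests are separate from it.

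The cost is the wording of one row and a little more analysis work on data already being collected. If the within-couple correlation is near zero, there is no gain.
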